10.3. Vital Signs

The following vital signs parameters will be recorded and summarized according to the Schedule of Time and Events in Section 14.2:

- Systolic blood pressure
- Diastolic blood pressure
- Pulse rate
- Body temperature
- Respiratory rate
- Weight

Vital signs values and change from baseline in vital signs values at all scheduled post-baseline assessment time points will be summarized via descriptive statistics by treatment group.

For summaries of body temperature, all measurements will be converted to oral equivalent. If the method of temperature collection is not available, the measurement will not be eligible for inclusion in the summary. Measurements will be converted to oral equivalent as follows:

- axillary temperature + 0.3°C = oral equivalent temperature
- rectal temperature – 0.5°C = oral equivalent temperature
- ear temperature – 0.5°C = oral equivalent temperature

Vital signs measurements will be evaluated by PCSV criteria, specifically identifying patients with at least 1 post-baseline measurement that meets the PCSV criteria (see Section 14.3). Patients meeting the PCSV criteria will be summarized by patient count (and percentage) for a post-baseline PCSV measurement by treatment group.

10.4. Electrocardiography

The following standard 12-lead electrocardiography (ECG) parameters will be recorded and summarized by treatment group according to the Schedule of Time and Events in Section 14.2:

- Mean heart rate
- P wave, R wave (PR) interval
- Q wave, R wave, S wave (QRS) duration
- Q wave, T wave (QT) interval
- QT interval corrected for heart rate using Bazett's formula (QTcB), where QTcB (ms) = QT/\sqrt{RR} , QT is the uncorrected QT interval measured in ms, and RR (the elapsed time between 2 successive R waves) is 60/HR with HR being the heart rate in beats per minute.
- QT interval corrected for heart rate using Fridericia's formula (QTcF), where QTcF (ms) = $QT/RR^{1/3}$, QT is the uncorrected QT interval measured in ms, and RR (the elapsed time between 2 successive R waves) is 60/HR with HR being the heart rate in beats per minute.
- RR interval
- Interpretation, i.e., overall ECG status along with findings.

ECG measurements and change from baseline at all scheduled post-baseline assessment time points will be summarized via descriptive statistics by treatment group.

ECG parameters will be evaluated by PCSV criteria, specifically identifying patients with at least 1 post-baseline measurement that meets the PCSV criteria (see Section 14.3). Patients meeting the PCSV criteria will be summarized by patient count (and percentage) for a post-baseline PCSV measurement by treatment group.

Shift tables will be constructed showing patients' transition in ECG status from baseline to specified post-baseline time points by treatment group. ECG status will be categorized as Normal, Abnormal (Not Clinically Significant), or Abnormal (Clinically Significant).

10.5. Other Safety Data

Summaries of COVID-19-related TEAEs (as identified by the Standardized MedDRA® Query (SMQ) for COVID-19 using narrow search criteria) will be presented by treatment group.

Additionally, the following summaries of conjunctivitis adverse events will be presented by treatment group:

- Treatment-emergent conjunctivitis AEs by primary SOC and PT using the Conjunctivitis Custom MedDRA® Query (CMQ) (Broad) search criteria specified in [Table 2](#)
- Treatment-emergent conjunctivitis AEs by primary SOC and PT using the Conjunctivitis CMQ (Narrow) search criteria specified in [Table 2](#)

Table 2: Additional Search Criteria for Conjunctivitis Adverse Events

Identifier	Search Criteria
Conjunctivitis CMQ (Broad)	CMQ10645 based on the following PTs: Conjunctivitis, Conjunctivitis allergic, Conjunctivitis bacterial, Conjunctivitis viral, Atopic keratoconjunctivitis, Blepharitis, Dry eye, Eye irritation, Eye pruritus, Lacrimation increased, Eye discharge, Foreign body sensation in eyes, Photophobia, Xerophthalmia, Ocular hyperaemia, Conjunctival hyperaemia
Conjunctivitis CMQ (Narrow)	CMQ10644 based on the following PTs: Conjunctivitis, Conjunctivitis allergic, Conjunctivitis bacterial, Conjunctivitis viral, and Atopic keratoconjunctivitis
Note: PTs included in this table are based on MedDRA® version 26.1. If a more recent version of MedDRA® is available and is used for reporting purposes, the PTs used in the programming logic for the search criteria will be updated accordingly.	
CMQ=custom MedDRA® query; MedDRA®=Medical Dictionary for Regulatory Activities; PT=preferred term.	

10.6. Immunogenicity Data

10.6.1. Immunogenicity Variables

The immunogenicity variables include ADA status, NAb status, and titer at nominal sampling times/visits. Serum samples for ADA will be collected at the clinic visits specified in Section 14.2. Samples positive in the ADA assay will be further characterized for ADA titers and for the presence of NAb.

10.6.2. Analysis of Immunogenicity Data

10.6.2.1. Analysis of ADA Data

The immunogenicity variables described in Section 10.6.1 will be summarized using descriptive statistics. Immunogenicity will be characterized per drug molecule by ADA status, ADA category, and maximum titer category observed in patients in the AAS analysis set. For samples confirmed as drug-specific ADA positive, but found negative at the lowest titer dilution, the lowest dilution in the titer assay is imputed.

The ADA status of each patient may be classified as one of the following:

- Positive
- Pre-existing - If the baseline sample is positive and all post-baseline ADA titers are reported as less than 4-fold the baseline titer value
- Negative - If all samples are found to be negative in the ADA assay

The ADA category of each positive patient is classified as:

- Treatment-boosted - A positive result at baseline in the ADA assay with at least one post-baseline titer result ≥ 4 -fold the baseline titer value
- Treatment-emergent - A negative result or missing result at baseline with at least one positive post-baseline result in the ADA assay. Patients that are treatment-emergent will be further sub-categorized as follows:
 - Persistent - A positive result in the ADA assay detected in at least 2 consecutive post-baseline samples separated by at least a 12-week post-baseline period [based on nominal sampling time], with no ADA-negative results in-between, regardless of any missing samples
 - Indeterminate - A positive result in the ADA assay at the last collection time point only, regardless of any missing samples
 - Transient - Not persistent or indeterminate, regardless of any missing samples

The maximum titer category of each patient is classified as:

- Low (titer $< 1,000$)
- Moderate ($1,000 \leq \text{titer} \leq 10,000$)
- High (titer $> 10,000$)

The following will be summarized by treatment group and ADA titer level:

- Number (n) and percent (%) of ADA-negative patients
- Number (n) and percent (%) of pre-existing patients
- Number (n) and percent (%) of treatment-emergent ADA positive patients
 - Number (n) and percent (%) of persistent treatment-emergent ADA positive patients
 - Number (n) and percent (%) of indeterminate treatment-emergent ADA positive patients
 - Number (n) and percent (%) of transient treatment-emergent ADA positive patients
- Number (n) and percent (%) of treatment-boosted ADA positive patients

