#### 9.1.1. Footnotes for the Schedule of Events Table

#### Footnotes for Table 1 Schedule of Events

\*Visits 5, 7, 9, and 10 will be performed as phone visits for patients not receiving OCS at baseline. For patients receiving OCS at baseline, these visits should be performed in-clinic if the patient remains on OCS on the day of the clinic visit. If OCS has been discontinued, these visits can be either in-clinic or performed as a phone visit at the discretion of the investigator. Assessments/procedures marked with an asterisk should only be performed if the visit occurs in-clinic.

\*\*After the last patient has completed visit 14/week 24 of the treatment period or withdrawn from the study, all patients still currently in the treatment period (between visit 15/week 26 and visit 27/week 50) should return to the clinic 2 weeks from their last dose/treatment administration to complete their EOT visit and all its applicable assessments. For patients who have withdrawn from the study treatment but remain in the study, the EOT visit will take place 2 weeks from their last visit. All patients must have their EOS visit 12 weeks after their EOT visit.

- a. Prior to screening, patients must be on a stable background therapy for asthma which may include ICS in combination with a second controller medication (eg, LABA, LTRA, theophylline, etc) for at least 3 months with a stable dose ≥1 month prior to baseline. Patients requiring a third controller are allowed to participate in this study. The third controller should also be used for at least 3 months with a stable dose ≥1 month prior to visit 1. Patients requiring systemic steroids of up to 10 mg per day (or up to 30 mg every alternate day) as controller medication are permitted.
- b. Randomization/baseline visit is defined as day 1. The visit schedule should be adhered to within  $\pm 1$  week for the screening period,  $\pm 3$  days for the randomized IMP treatment period, and  $\pm 7$  days for the post-IMP treatment period.
- c. All assessments at visit 2 (day 1) are to be conducted pre-IMP dose except for the assessment of local tolerability of SC injections.

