11.4. Unscheduled Assessments and Assignment of Data to Visit Windows

Unscheduled Assessments

The determination of values for by-visit analyses for both efficacy and safety variables will be based on assessments available from scheduled visits, or from unscheduled visits if the scheduled visit was not performed.

Extra assessments (e.g., laboratory data or vital signs associated with non-protocol-specified visits or obtained in the course of investigating or managing AEs) will be included in data listings, but not in summaries except for the endpoint determination. If more than one laboratory value is available for a given visit, the first observation will be used in summaries.

Assignment of Data to Visit Windows

Data analyzed by visit (including efficacy, laboratory, vital signs, ECG, ADA, etc.) will be summarized by the study scheduled visits described in the Schedule of Time and Events in Appendix 14.2.

The analysis visit windows are created per the Schedule of Time and Events for each parameter and will only be applied if the data from the study scheduled visits are unavailable. The following general, hierarchical rules will be applied for mapping the unscheduled visits and/or the early termination visit, EOT visit, or EOS visit (which will subsequently be collectively referred to as the “early termination of treatment or study” [ETTS] visit) for each parameter.

Note that the EOT visit is coded as “Week 52/ Visit 28” for all patients, regardless of the variable 24-52-week treatment period.

1. If the ETTS visit falls in an analysis window which already has an observed value of the parameter from the scheduled visit, the ETTS visit will be mapped to the next scheduled visit, provided there is no observed value of the parameter at the next scheduled visit.
2. If there is no observed value of the parameter from the scheduled visit and if both the ETTS visit and 1 or more unscheduled visits of the parameter are available in the same analysis visit window, only the ETTS visit may be mapped to a scheduled visit.
 - a. Note: If at least 2 of the EOT, EOS, and early termination visits are available in the same analysis visit window, then the ETTS visit to be mapped to the scheduled visit will be selected in the following hierarchical order: EOT visit, EOS visit, early termination visit.

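### Persistent ADA is judged on nominal time while every EOT is coded Week 52, so positive samples 2 to 10 weeks apart can count as 28 weeks apart

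*SAP*

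**What the plan says.** - **Persistence rule (SAP 10.6.2.1).** A treatment-emergent patient is persistent if at least two consecutive post-baseline samples are ADA-positive, "separated by at least a 12-week post-baseline period [based on nominal sampling time", with no negative result between them. Indeterminate means positive at the last collection point only. Transient is everything else.
- **EOT code (SAP 11.4).** "Note that the EOT visit is coded as “Week 52/ Visit 28” for all patients, regardless of the variable 24-52-week treatment period".
- **Real EOT timing (Protocol, footnotes to Table 1).** "After the last patient has completed visit 14/week 24 of the treatment period or withdrawn from the study", patients still on treatment "should return to the clinic 2 weeks from their last dose/treatment administration to complete their EOT visit". A last dose at Week 24 therefore puts EOT at Week 26. Also, "All patients must have their EOS visit 12 weeks after their EOT visit".
- **ADA sampling (Protocol Table 1; SAP 14.2).** Weeks 0, 12 and 24, EOT and EOS.
- **Visit mapping (SAP 11.4 and Table 3).** The by-visit rules name ADA among the data they cover. The ADA windows are days 127 to 210 for Week 24 and days 211 to 462 for Week 52. If the window already holds a scheduled value, "the ETTS visit will be mapped to the next scheduled visit, provided there is no observed value of the parameter at the next scheduled visit".

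**The concern.** The 12-week criterion is meant to separate a lasting antibody response from a short one. Nominal time serves that purpose when every patient has EOT at Week 52. Under the variable treatment period, EOT can come as early as two weeks after the Week 24 sample, yet its nominal week stays at 52. Two positives close together then meet a 12-week test that they fail in calendar time.

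The error for a Week 24/EOT pair runs one way, from transient to persistent, and only in patients whose treatment was shortened. Protocol 11.4.6 commits to reporting the incidence of persistent response, and SAP 10.6.2.1 tabulates persistent and transient counts by treatment group. SAP 10.6.3.1 may also use ADA category when examining concentration profiles.

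**Working it through.** **Inputs.** Target days 169 (Week 24) and 365 (Week 52) and the ADA windows come from SAP Table 3. The sampling weeks come from Protocol Table 1, and the EOT and EOS timing from its footnotes.

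**1. Reproduce the SAP's target days.** Day = 7 × week + 1 gives 169 for Week 24 and 365 for Week 52, as in Table 3. Nominal gap = (365 − 169)/7 = 28 weeks.

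**2. Real gap by EOT week.** Gap = EOT week − 24; EOS week = EOT week + 12.

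| EOT week | EOT day | EOS day | Real gap (weeks) | Gap with EOT coded Week 52 | Where Table 3 puts EOT |
|---|---|---|---|---|---|
| 26 | 183 | 267 | 2 | 28 | Week 24 window; Week 52 contested by EOS |
| 28 | 197 | 281 | 4 | 28 | Week 24 window; Week 52 contested by EOS |
| 30 | 211 | 295 | 6 | 28 | Week 52 |
| 32 | 225 | 309 | 8 | 28 | Week 52 |
| 34 | 239 | 323 | 10 | 28 | Week 52 |
| 36 | 253 | 337 | 12 | 28 | Week 52 |

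From Week 36 on, the real gap is at least 12 weeks and the two time bases give the same class.

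**3. Does Table 3 settle the label?**
- From day 211, EOT lies in the Week 52 window. EOS lies there too, but rule 2a in SAP 11.4 ranks EOT ahead of EOS within one window, so EOT takes Week 52.
- On day 183 or 197, EOT lies in the Week 24 window, which already holds the Week 24 sample. Rule 1 moves it to Week 52 only if no value is observed there. EOS (day 267 or 281) falls in the Week 52 window, and the rules do not say which sample takes it. If a negative EOS does, the mapped sequence is positive then negative, which is transient. If EOS is missing, nothing competes and EOT moves to Week 52.
- Day 211 is exactly Week 30. A Week 30 EOT done 1 to 3 days early (days 208 to 210) behaves like the Week 26 and 28 cases.

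**4. Which result patterns change class?** All 81 combinations of positive, negative and missing at Weeks 12 and 24, EOT and EOS were classified twice. Nominal weeks were 12, 24, 52 and 64; real weeks were 12, 24, e and e + 12, where e is the EOT week. For each e from 26 to 34 the same four patterns differ: Week 24 and EOT positive, Week 12 negative or missing, EOS negative or missing. For e of 36 or more, none differ. A positive Week 12 or EOS makes the patient persistent either way, because 24 − 12 = 12 and EOS − EOT = 12.

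**5. Size.** One patient among about 30 on dupilumab is 1/30 = 3.3 percentage points. The documents do not give the number exposed, so the following rests on assumptions. Exposure needs randomization less than about 10 weeks before the last patient. Protocol 3.3.1 counts 37 ABPA patients at 28 March 2022, and Amendment 3 says nearly 60 when enrollment stopped, which leaves about 23. If these accrued evenly over 6 to 12 months, 23 × 10/26 = 8.8 to 23 × 10/52 = 4.4 patients are exposed, so about 2 to 4 on dupilumab. If 5% to 10% of those show the pattern, the expected number misclassified is 2 × 0.05 = 0.1 to 4 × 0.10 = 0.4.

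**The case against.** The strongest reply is that the SAP never defines nominal sampling time. SAP 10.6.1 speaks of nominal sampling times or visits and points to the schedule in Section 14.2, where EOT is shown as Week 24-52. The Week 52 note sits among the by-visit rules, and persistence is a patient-level category. This stands as a reason not to call the misclassification certain. It does not remove the problem: a range cannot be used to compute a gap, and Week 52 is the only single week the SAP gives EOT, under rules that name ADA.

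A reader might infer that Table 3 independently assigns Week 52 to every early EOT. It does not for EOT at Weeks 26 and 28, because EOS competes for that window.

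A reader might also infer that secondary endpoint 11 as a whole is compromised. It is not. Treatment-emergent and treatment-boosted incidence, titer and NAb status are unchanged, and the safety and efficacy associations in SAP 10.6.3.2 do not use the persistent/transient split.

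Finally, switching to actual dates is not free of difficulty. Week 12/24 and EOT/EOS are exactly 12 weeks apart by schedule, so any tolerance for visit windows decides their class. With EOS missing, a short Week 24/EOT pair would become transient although both last samples were positive. Both points stand and shape the fix.

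**Conclusion.** The concern holds in a limited form. On the most natural reading of SAP 10.6.2.1 with 11.4, a Week 24/EOT positive pair with EOT at Weeks 26 to 34 is credited with 28 weeks when 2 to 10 have passed. With Week 12 negative or missing and EOS negative, the patient is classed as persistent instead of transient. Table 3 supports this for EOT from day 211 on; at Weeks 26 and 28 it depends on the visit code.

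The conclusion assumes that nominal time means the coded visit week. It does not arise if Visit 14 (Week 24) is itself the EOT, since there is then only one sample. The output is descriptive, carries no test, and does not touch the primary endpoint. Few patients, possibly none, will be affected. It is a small correction worth making.

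**What to change.** Add to SAP 10.6.2.1: for the persistence rule, EOT, EOS and early-termination samples take their true scheduled week, meaning the every-2-weeks visit week closest to the actual collection date, with EOS set to the EOT week plus 12. The Week 52 code and the Table 3 mapping do not apply to this rule. Early termination belongs in the sentence because, under rule 1, a sample at about Week 14 (day 99) with Week 12 already filled maps to Week 24 and would count as 12 weeks apart instead of about 2.

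An alternative is actual dates with one stated tolerance, for example at least 74 days (84 − 3 − 7), which keeps on-schedule Week 12/24 and EOT/EOS pairs. It is slightly less clean: a Week 24 sample 3 days early and a Week 34 EOT 3 days late are 242 − 166 = 76 days apart and would pass.

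State also how Week 24 positive, EOT positive and EOS missing is classed when the gap is under 12 weeks, since resolution was not observed.

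The cost is a little extra derivation work. No new data are needed: SAP Section 4 already uses the date and time of ADA samples to set baseline.

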10.6.2.2. Analysis of NAb Data

The absolute occurrence (n) and percent (%) of patients with each NAb status in the NAS analysis set will be provided by treatment group. The NAb status is categorized as follows:

- Negative – Samples tested negative in the ADA assay, or samples positive in the ADA assay but tested negative in the NAb assay
- Positive – Samples tested positive in the NAb assay

10.6.3. Association of Immunogenicity with Exposure, Safety and Efficacy

10.6.3.1. Immunogenicity and Exposure

Potential association between immunogenicity variables and systemic exposure to dupilumab will be explored by treatment group. Plots of individual concentration time profiles may be provided to examine the potential impact of ADA category, maximum titer category, and NAb status on these profiles.

10.6.3.2. Immunogenicity and Safety and Efficacy

Potential association between immunogenicity variables and safety may be explored with a primary focus on the following safety events during the treatment-emergent period:

- Injection site reaction (serious or severe and lasting 24 hours or longer)
- Hypersensitivity (SMQ: Hypersensitivity [Narrow])
- Anaphylaxis (SMQ: Anaphylactic Reaction [Narrow])

Potential association between immunogenicity variables and efficacy endpoints may be explored (e.g., scatter plot or spaghetti plot).

The safety and efficacy analyses mentioned above will be conducted using the following categories:

- ADA Positive
 - Treatment-emergent
 - Treatment-boosted
- Maximum post-baseline titer category in ADA positive patients
- NAb positive

10.7. Pharmacokinetic Data

PK analyses will be performed on the PKAS.

Serum samples for measuring functional dupilumab concentrations will be collected at time points according to Section 14.2. PK parameters may include, but are not limited to, C_{trough} and $C_{trough,ss}$.

The following analyses will be conducted:

- Descriptive statistics of functional dupilumab concentrations in serum at each sampling time by dose
- Graphical presentations of median and mean (+/- SD) functional dupilumab concentration in serum vs. nominal time
- Graphical presentations of individual functional dupilumab concentration in serum vs. actual sampling time
- Assessment of the impact of anti-drug antibodies on functional dupilumab concentrations in serum

No formal statistical analysis will be performed.

11. DATA CONVENTIONS

11.1. Definition of Baseline for Efficacy/Safety Variables

The definition of baseline measurements for efficacy and safety variables is provided in Section 4.

11.2. Data Conventions

Adverse Events Data Analysis Conventions

Severity

Frequency tables of severity by TEAE will display only the maximum severity experienced by each patient for each unique AE preferred term. If no severities are recorded for a given preferred term for a patient, the severity will be classified as “Missing” in the frequency tables of severity by TEAE.

Adverse Event Start Date

The AE start date will be used for AE classification (i.e., determining whether the AE is treatment-emergent). If the AE start date is not complete, then, in the analysis dataset, the character variable will keep the original incomplete date, the numerical date variable will be imputed, and an imputation flag will be derived to indicate which date component is missing. Note that if the AE start date is not complete, any time information that is available will be ignored for the purposes of analysis (e.g., will not be used to determine if an AE is treatment-emergent).

If the AE start day is missing and the AE start month and year are not missing:

- If the AE start year is the same as the year of the first dose of study drug and the AE start month is the same as the month of the first dose of study drug, then the AE start day is imputed as the day of the first dose of study drug. If this results in a date after the AE end date, impute the AE start date as the AE end date instead.
- Otherwise, impute the AE start day as “01”. If this results in a date prior to the date of initial informed consent/assent, the AE start date will be imputed to be the date of initial informed consent/assent instead.
- The imputation flag is set to “D”.

If the AE start month is missing and the AE start year is not missing:

- If the AE start year is prior to the year of the first dose of study drug, impute the AE start day and month as the day and month of the initial informed consent/assent.
- If the AE start year is equal to the year of the first dose of study drug, impute the AE start day and month as the day and month of the first dose of study drug. If this results in a date after the AE end date, impute the AE start date as the AE end date instead.
- If the AE start year is after the year of the first dose of study drug, impute the AE start day and month as “01 January”.
- The imputation flag is set to “M”.

If the AE start year is missing:

- Impute the AE start date as the date of the first dose of study drug. If this results in a date after the AE end date, impute the AE start date as the AE end date instead.
- The imputation flag is set to “Y”.

Adverse Event End Date

The general recommendation is to not impute the AE end date. However, since the AE end date will be used in the programming logic for the imputation of the AE start date, the following intermediate steps will be used.

If the AE end day is missing and the AE end month and year are not missing:

- Impute the AE end day as the last day of the month. If this results in a date after the date of last patient contact, impute the AE end date as the date of last patient contact instead.

If the AE end month is missing and the AE end year is not missing:

- Impute the AE end day and month as “31 December”. If this results in a date after the date of last patient contact, impute the AE end date as the date of last patient contact instead.

If the AE end year is missing:

- Impute the AE end date as the date of last patient contact.

Only the original character/numeric AE end date recorded in the Adverse Event eCRF will be kept in the final analysis dataset (i.e., imputed AE end dates will not be retained in the final analysis dataset).

Prior and Concomitant Medications Data Analysis Conventions

To determine whether a medication is a prior (i.e., pre-treatment) medication or a concomitant medication (or both), incomplete medication start dates will be imputed to be as early as possible and incomplete medication end dates will be imputed to be as late as possible. If the medication start/end date is not complete, then, in the analysis dataset, the character variable will keep the original incomplete date, the numerical date variable will be imputed, and an imputation flag will be derived to indicate which date component is missing.

Prior Medication Start Date

If the medication start day is missing and the medication start month and year are not missing, impute the medication start day as “01”. The imputation flag is set to “D”.

If the medication start month is missing and the medication start year is not missing, impute the medication start day and month as “01 January”. The imputation flag is set to “M”.

If the medication start year is missing, impute the medication start date to be 1 year prior to the date of initial informed consent/assent. The imputation flag is set to “Y”.

Note: For medications with missing start year, the general recommendation is to not impute the medication start date. However, to simplify the programming logic, the imputation proposed is aligned with the CCG, which specifies to collect all medications given within 12 months prior to the screening visit.

Prior Medication End Date

If the medication end day is missing and the medication end month and year are not missing, impute the medication end day as the last day of the month. If this results in a date on or after the date of the first dose of study drug, impute the medication end date as the date of the first dose of study drug -1 instead. The imputation flag is set to “D”.

If the medication end month is missing and the medication end year is not missing, impute the medication end day and month as “31 December”. If this results in a date on or after the date of the first dose of study drug, impute the medication end date as the date of the first dose of study drug -1 instead. The imputation flag is set to “M”.

If the medication end year is missing, impute the medication end date as the date of the first dose of study drug -1. The imputation flag is set to “Y”.

Concomitant Medication Start Date

The rules for imputing the concomitant medication start date are the same as those described above for imputing the AE start date.

Concomitant Medication End Date

If the medication end day is missing and the medication end month and year are not missing, impute the medication end day as the last day of the month. If this results in a date after the date of last patient contact, impute the medication end date as the date of last patient contact instead. The imputation flag is set to “D”.

If the medication end month is missing and the medication end year is not missing, impute the medication end day and month as “31 December”. If this results in a date after the date of last patient contact, impute the medication end date as the date of last patient contact instead. The imputation flag is set to “M”.

If the medication end year is missing, impute the medication end date as the date of last patient contact. The imputation flag is set to “Y”.

Medication Coding Data Analysis Conventions

Medications whose ATC level 4 cannot be coded will be summarized by setting ATC4=ATC2. However, these unencoded ATC level 4 records need to be confirmed with the study data manager and medical director.

Potentially Clinically Significant Values Data Analysis Conventions

Patients who had a post-baseline PCSV but are missing the baseline value will be regarded as having a treatment-emergent PCSV.

